9.7.2.4.3 Exploratory Outcome Measure

Descriptive summaries of PAM 13 scores will be presented.

9.7.2.5 Sensitivity Analysis

A sensitivity analysis to explore the effect of influential subgroups (eg country, clinical characteristics) on the primary outcome measure may be conducted, if appropriate.

9.7.2.5.1 Subgroup Analysis

Subgroup analysis will be conducted to be supportive of the analysis of the primary, secondary and exploratory endpoints. The subgroup analysis will be the planned analysis stratified by country.

9.7.3 Analysis of Safety Outcomes

No formal analysis of Safety data is planned for this study.

9.8 Quality Control

Source data verification will be performed at the study site, in accordance with ICTU SOPs.

The Investigator is to maintain a list of appropriately qualified persons to whom he/she has delegated study duties. All persons authorized to make entries and/or corrections on CRFs will be included on the Delegation of Authority Form.

Source documents are original documents, data, and records from which the subject's eCRF data are obtained. These include but are not limited to hospital records, clinical and office charts, laboratory and pharmacy records, diaries, microfiches, radiographs, and correspondence.

The Investigator and study staff are responsible for maintaining a comprehensive and centralized filing system of all study-related (essential) documentation, suitable for

inspection at any time by representatives from ICTU, Amgen and/or applicable regulatory authorities.

Elements to include:

- Subject files containing completed eCRF, informed consent forms, as applicable, and subject identification list
- Study files containing the protocol with all amendments, copies of pre-study documentation, and all correspondence to and from the IRB/IEC or other relevant ethical review board and ICTU

In addition, all original source documents supporting entries in the eCRFs must be maintained and be readily available.

Retention of study documents will be governed by the contractual agreement with ICTU.

Amgen retains all data, programmes and outputs generated for the study. At data cleaning completion, data are uploaded from InForm, transferred to Amgen and stored in accordance with Amgen SOPs. Statistical programming and outputs are locked in the analysis environment and no updates are permitted; standard programming procedures will apply.

9.9 Limitations of the Research Methods

9.9.1 Internal Validity of Study Design

9.9.1.1 Information Bias

For the primary objective, information bias is not anticipated to be applicable, as having an LDL-C measurement within the 14 months preceding enrolment is an Inclusion criterion; if several measurements are available then the two most recent to enrolment will be reported and used in the study analysis.

For the secondary objectives, LMT use is an Inclusion criterion so reliable prescription details will be known and reported by the Investigator. It is also expected that Investigators will be well aware of variables concerning the secondary objectives around clinical characteristics and other laboratory values, as typically these are well documented and the subjects will be known to the Investigators.

Information bias may arise in recording reasons for LMT regimen change and/or history of statin intolerance, as these are more liable to be subjective and based on individual judgement; accurate and truthful reporting is encouraged in the eCRF through provision of a range of pre-populated response options and a free text field for Investigator comments. Interpretation of these objectives should take these factors into account.

9.9.1.2 Selection Bias

Inclusion/exclusion criteria are sufficiently broad to allow enrolment of a variety of subjects, although the potential difficulty in achieving the ideal balance of primary and secondary prevention subjects, whilst enriching for PVD and IS subjects, from primary and secondary care sites, is acknowledged. Care in site selection, as described in [Section 9](#), is critical to success in this regard.

At the site level, to avoid enrolment bias via selective invitation of a particular subject profile to participate in the study, all eligible patients will be invited to enrol in chronological order of attending the clinic, until the local enrolment cap has been reached. This also minimises selection of study subjects based on Investigator preference.

9.9.1.3 Confounding

N/A

9.9.2 External Validity of Study Design

The broad eligibility criteria are intended to prevent exclusion of particular disease groups and to encourage enrolment of as diverse a subject population as possible. The geographic spread (across approximately 18 EU countries) and inclusion of subjects from both primary and secondary care are designed to provide a representative sample of EU patients receiving lipid modifying therapy. The study population will comprise both primary and secondary prevention subjects, of differing CV risk, and the intent is that this study sample reflects the wider background population who are prescribed LMT.

However, regional health authorities' access policies will determine which patients are eligible for LMT prescription, and this will have a bearing on the clinical characteristics of subjects in different locations. In addition, the study will not enrol patients receiving LMT but who do not have a recent (within 14 months) LDL-C measurement, so will miss patients who may be less well managed in routine care. As the primary objective of the study is to provide a picture of contemporary lipid management to ESC target, this limitation is unavoidable and will be taken into account in interpretation of the data.

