9.1 Study Design

The study is a multicountry, cross-sectional, observational study of routine clinical management of European patients in primary and secondary care, who may be at elevated risk of cardiovascular event. The cross-sectional design is appropriate to provide a contemporary landscape assessment of the clinical management of this patient population.

All data will be collected at the time of the clinic visit. The subject is considered to have been enrolled when written informed consent has been obtained (if required by local practice), eligibility has been confirmed and subject data entry into the eCRF has begun.

The study electronic database (InForm) is built and provided to sites by Imperial College Trials Unit (ICTU).

There are no formal visits or assessments required as part of the study, although subjects will be invited to complete the PAM 13 questionnaire ([Appendix F](#)) if permitted by local practice to do so as part of an observational study. The questionnaire will be self-administered by the subject on a device provided to the site, and subject responses will be downloaded remotely to be scored by the PRO provider (Insignia Health). If a subject is unable or unwilling to complete the PAM 13, the remainder of the subject's study data will still be analysed as normal.

This is a non-interventional, observational study and is not intended to alter the clinical management of patients.

It is intended that at least half of the subjects enrolled will be classified as primary prevention patients, ie, are without established ASCVD. The remainder will be classified as secondary prevention patients (as evidenced by a diagnosis of established ASCVD prior to enrolment).

Enrolment will not be formally stratified by clinical characteristics; site selection (secondary vs primary care physicians) and site enrolment caps will be employed to facilitate enrolment of the required proportion of primary and secondary prevention subjects.

In addition, being cognisant of the paucity of data available on patients with a history of PVD and IS as compared to MI, the optimal enrolment ratio of MI:PVD:IS subjects is 1:2:2. This ratio will be sought by selection of appropriate specialist sites (see [Section 9.2.2](#) below).

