9.2.2 Selection and Number of Sites

Site selection:

- Will be carried out according to normal feasibility and selection processes
- Will evaluate both primary and secondary care sites:
- At least 25% of sites will be primary care
- Secondary care sites will be selected proportionately according to speciality, to enable enrolment of a study population enriched for PVD and IS subjects
- Will require sites to demonstrate the ability to provide adequate study data ie, demographics and CV history, at least one LDL within the pre-specified window, and the previous/current LMT regimen

Selection is based on interest in participation as a study site, and willingness and ability to meet the criteria above, and to comply with the protocol and data entry conventions.

It is expected that approximately 160 sites will be selected, across approximately 18 EU countries.

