9.3 Variables

Individual site characteristics:

- Primary care/ secondary care/ speciality
- Number of patients with each relevant study indication seen per year
- Number of patients with each relevant study indication who are prescribed LMT during the conduct of the study
- Lipid guidelines followed at site (and if Yes then which ones)
- Previous/current experience of lipid-lowering RCT conduct

Subject level:

- Referral to study physician (eg referred from specialist or GP, and date referred)
- Demographics (gender, age at enrolment, ethnicity if permitted to record)
- Relevant medical history (CV events including dates, known risk factors [smoking, family history], diabetic/hypertension/renal/rheumatoid arthritis status, vascular bed involvement)
- Participation in a clinical study within previous 12 months
- Height/weight/BP/waist circumference
- Lipid profile (including fasting status) (total cholesterol, LDL, HDL, non-HDL, triglycerides, Lp(a), apo B100, apo A1), HbA1c, plasma glucose (including fasting status)
- LMT (type, dose, dose frequency, duration of prescription) at enrolment; in 12 months prior to enrolment, up to and including enrolment date
- History of intolerance to higher doses than currently, or to other statins
- Reason for prescription if non-ASCVD (eg diabetic, CKD, subject request)
- Other concomitant therapies of interest (antihypertensives, antidiabetics, antiplatelets, acetylsalicylic acid)

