9.7.2.4 Analysis of the Primary, Secondary and Exploratory Outcome Measures

9.7.2.4.1 Analysis of Primary Outcome Measure

Summaries displaying the frequency and percentage with 95% confidence interval will be presented for LDL-C within or above the 2016 Joint ESC Guideline-recommended targets. Subjects will be presented overall and split into subgroups with and without established ASCVD.

Subjects included in the secondary prevention cohort will fulfil the following:

- Documented history of MI or revascularisation (peripheral, carotid or coronary), ischaemic stroke, or symptomatic PVD, as defined in [Appendix B](#), except for patients diagnosed with familial hypercholesterolaemia (FH).
- Subjects without a history of MI or revascularisation are eligible if they have DOCUMENTED angiographic evidence of atherosclerosis defined as $\geq 30\%$ stenosis in at least one coronary artery using either standard coronary angiography or CT coronary angiography.

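### The protocol enriches its sample by design but describes it as reflecting EU patients on LMT, so the overall and pooled ASCVD percentages can be over-read

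*Protocol*

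**What the plan says.** All references are to the Protocol.

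**How the mix is steered.** Section 9.1 sets two aims for composition. For prevention status: "It is intended that at least half of the subjects enrolled will be classified as primary prevention patients". Within vascular disease: "the optimal enrolment ratio of MI:PVD:IS subjects is 1:2:2". The stated reason for the second is that less is known about PVD and IS than about MI. Enrolment is not formally stratified. The balance between the two prevention cohorts is pursued by other means: "site selection (secondary vs primary care physicians) and site enrolment caps will be employed to facilitate enrolment of the required proportion". Section 9.2.2 adds that secondary care sites are chosen by speciality "to enable enrolment of a study population enriched for PVD and IS subjects", and sets a floor for care setting: "At least 25% of sites will be primary care".

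**How the result is reported.** Section 9.7.2.4.1 gives frequency, percentage and 95% confidence interval for LDL-C within or above target: "Subjects will be presented overall and split into subgroups with and without established ASCVD". The protocol mentions no weighting or standardisation. The sensitivity analysis in section 9.7.2.5 is optional.

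**What is claimed for the sample.** Section 9.9.2 presents the geographic spread and the two care settings as giving a representative sample of treated EU patients, and adds that "the intent is that this study sample reflects the wider background population who are prescribed LMT". It names two limits: regional access policies, and the omission of patients without a recent LDL-C. Section 9.9.1.2 mentions the enrichment only as a recruitment difficulty. Section 9.9.3 refers the reader to the missing-data section.

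**The concern.** A sample enriched on purpose for two indications is not meant to mirror the population it comes from, so the aims in sections 9.1 and 9.2.2 conflict with the statement in section 9.9.2. Inviting patients consecutively within a site (section 9.9.1.2) prevents selection by the investigator. It does not correct a mix that arises from which sites were chosen.

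The primary objective is a proportion among patients in EU primary and secondary care, and section 7 expects the results to measure the gap between guideline and practice and to inform policy. A reader who accepts section 9.9.2 will take the overall and pooled ASCVD percentages as population figures. If attainment differs between MI, PVD and IS, or between primary and secondary prevention, those two percentages partly reflect the recruitment targets. A larger sample narrows the interval without removing that dependence.

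**Working it through.** **1. The plan's own precision.** Section 9.5, Table 2 assumes 50%. The half-width is 100 × 1.96 × √(0.25/n):

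| n | Table 2 | Recomputed |
|---|---|---|
| 70 | 11.7 | 11.71 |
| 100 | 9.8 | 9.80 |
| 130 | 8.6 | 8.60 |
| 150 | 8.0 | 8.00 |
| 200 | 6.9 | 6.93 |
| 250 | 6.2 | 6.20 |
| 300 | 5.7 | 5.66 |

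All seven agree, so the stated precision is that of an unweighted simple random sample. The same formula gives 1.27 points at n=6000 (the planned total) and 1.79 at n=3000 (half of it).

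**2. Inputs for the mix effect.**
- From section 9.1: 1:2:2, i.e. 20% MI, 40% PVD, 40% IS among these three groups; primary prevention taken at its floor of 50%.
- Assumed, because the documents give no figures: a population MI share *m* of 33 to 60%, the rest split equally between PVD and IS; population primary-prevention shares *s* of 40, 60, 70 and 80%; a gap *g* of 5 to 20 points in the proportion above target, between MI and PVD/IS or between the two prevention cohorts. MI, PVD and IS are treated as non-overlapping.

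**3. Pooled ASCVD figure.** The crude mean uses shares 0.2/0.4/0.4 and the population mean uses *m* and (1−*m*). The difference is *g* × (*m* − 0.2):

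| m | g = 5 | g = 10 | g = 20 |
|---|---|---|---|
| 33% | 0.7 | 1.3 | 2.7 |
| 40% | 1.0 | 2.0 | 4.0 |
| 50% | 1.5 | 3.0 | 6.0 |
| 60% | 2.0 | 4.0 | 8.0 |

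Eight of the 12 cells exceed 1.79 points. The direction depends on which group has the worse attainment, which the documents do not say.

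These shifts are upper values for the ASCVD cohort in one respect. Section 9.7.2.4.1 also admits subjects who qualify only through coronary or carotid revascularisation, or through angiographic stenosis. They lie outside the ratio. If they form a fraction *f* of both the sample and the population, with the same rate in each, every shift is multiplied by (1−*f*).

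**4. Overall figure.** The difference is *g* × |*s* − 0.5|:

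| s | g = 5 | g = 10 | g = 20 |
|---|---|---|---|
| 40% or 60% | 0.5 | 1.0 | 2.0 |
| 70% | 1.0 | 2.0 | 4.0 |
| 80% | 1.5 | 3.0 | 6.0 |

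It is zero if the enrolled share happens to equal the population share. Counting 40% and 60% separately, seven of 12 scenarios exceed 1.27 points.

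**5. Cost of standardising.** The Kish design effect is Σ(population share² / design share).
- ASCVD, *m* = 33%: 0.111/0.2 + 2 × 0.111/0.4 = 1.11. *m* = 60%: 0.36/0.2 + 2 × 0.04/0.4 = 2.00. The half-width at n=3000 becomes 1.89 to 2.53.
- Overall, *s* = 40%: 0.16/0.5 + 0.36/0.5 = 1.04. *s* = 80%: 0.64/0.5 + 0.04/0.5 = 1.36. The half-width at n=6000 becomes 1.29 to 1.48.

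**The case against.** The best defence is that the protocol already does much of what is needed.

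- **The split by ASCVD status.** The data-analysis paragraph of the Abstract (section 4) says the proportion is to be estimated separately with and without ASCVD, and section 9.7.2.4.1 repeats the split. This stands: the primary/secondary mix cannot affect the two split figures. It still affects the overall figure, and the split leaves the MI:PVD:IS mix inside the ASCVD figure.
- **Subgroups.** Section 9.7.2.4.2 firmly plans attainment by clinical characteristics, among which it lists ASCVD components. This also stands, but as a secondary look at predictive factors; it does not qualify the pooled figure.
- **The SAP.** Weights could be specified there. That is fair, and their absence from the protocol is not the point. A SAP would not remove the statement in section 9.9.2.

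Four stronger readings are tempting and are not supported:

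- That caps fix the primary-prevention share at half. Section 9.1 says at least half, without formal stratification, and the 1:2:2 ratio is an optimum to be sought. Section 9.9.1.2 concedes that the balance may be hard to reach.
- That the protocol calls its pooled percentages representative. Section 9.9.2 states an intent for the sample; the step to the percentages is the reader's.
- That attainment is known to differ by indication. The reason given for enrichment is scarcity of data, which says nothing about attainment.
- That the site-level item in section 9.3 ("Number of patients with each relevant study indication who are prescribed LMT during the conduct of the study") could supply the weights. Those counts describe participating sites, themselves chosen for speciality, interest and ability. They would restore the case mix of those sites and leave the distortion between sites in place.

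**Conclusion.** The point holds as an internal contradiction. The protocol plans an enriched sample and, in section 9.9.2, gives that sample a property its design does not aim for, without listing enrichment as a limit on generalisation. The consequence is confined to the overall and pooled ASCVD percentages, and is conditional on attainment differing between the groups concerned.

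The documents do not fix the size. Under the stated assumptions it is 0.7 to 8.0 points for pooled ASCVD, less once subjects outside MI, PVD and IS are counted, and 0.5 to 6.0 points overall at the four assumed population shares. In many of these scenarios the shift exceeds the simple-random-sampling half-width, and in the mildest it does not. This limits what the pooled figures can be used to conclude; it does not invalidate the study or the figures reported by cohort.

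**What to change.** - **Section 9.9.2.** Replace the two sentences on representativeness with a statement that the sample is enriched by design for PVD and IS and steered towards at least half primary prevention. List this as a limitation beside access policies and missing recent LDL-C.
- **Section 9.7.2.4.1.** State that the unweighted overall and pooled ASCVD percentages describe the enrolled mix only. Make the results with and without ASCVD, and MI, PVD and IS separately within ASCVD, the main presentation. Say how subjects with more than one of these histories are counted.
- **Only if a population-level pooled figure is wanted.** Standardise to pre-specified population shares from an external source, with a variance to match. The section 9.3 site counts alone are not enough.

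The first two changes are text and table order, and the protocol already plans to record CV history and vascular bed involvement. The third costs precision: a design effect of about 1.1 to 2.0 for ASCVD and 1.04 to 1.36 overall under the assumptions above. It also needs an external source that the protocol does not name.

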9.9.3 Analysis Limitations

See [Section 9.9.4](#) below.

9.9.4 Limitations Due to Missing Data and/or Incomplete Data

Missing/incomplete data is a possibility on this study, but is not expected to be significant: Key variables of LDL-C and LMT are inclusion criteria so cannot be missing.

Subjects are expected to be followed closely by their specialist physicians and the variables collected in the eCRF are those captured as part of routine care of this patient population. Additionally, ICTU will review all study data thoroughly on an ongoing basis throughout the study conduct period, and will follow up directly with study sites to query for information which seems to be missing from InForm.

9.10 Other Aspects

N/A

10. Protection of Human Subjects

10.1 Informed Consent

An initial sample informed consent form is provided for the Investigator to prepare the informed consent document to be used at his or her site. Updates to the template are to be communicated formally in writing from the ICTU Study Manager to the Investigator. The written informed consent document is to be prepared in the language(s) of the potential subject population.

Before a subject's participation in the study, the Investigator is responsible for obtaining written informed consent, where applicable by local regulations, from the subject or legally acceptable representative after adequate explanation of the aims, methods, anticipated benefits, and potential hazards of the study and before any protocol-specific activities/assessments are conducted. A legally acceptable representative is an individual or other body authorized under applicable law to consent, on behalf of a subject, to the subject's participation in the study.

The acquisition of informed consent and the subject's agreement or refusal of his/her notification of the primary care physician is to be documented in the subject's medical records, and the informed consent form is to be signed and personally dated by the subject or a legally acceptable representative and by the person who conducted the informed consent discussion. The original signed informed consent form is to be retained in accordance with institutional policy, and a copy of the signed consent form is to be provided to the subject or legally acceptable representative.

If a potential subject is illiterate or visually impaired and does not have a legally acceptable representative, the Investigator must provide an impartial witness to read the informed consent form to the subject and must allow for questions. Thereafter, both the subject and the witness must sign the informed consent form to attest that informed consent was freely given and understood.

10.2 Institutional Review Board (IRB)/Independent Ethics Committee (IEC)

An initial sample informed consent form is provided for the Investigator to prepare the informed consent document to be used at his or her site. Updates to the template are to be communicated formally in writing from ICTU to the Investigator. The written informed consent document is to be prepared in the language(s) of the potential subject population.

Before a subject's participation in the study, the Investigator is responsible for obtaining written informed consent, where applicable by local regulations, from the subject or legally acceptable representative after adequate explanation of the aims, methods, anticipated benefits and potential hazards of the study, and before any protocol-specific activities/assessments are conducted. A legally acceptable representative is an individual or other body authorized under applicable law to consent, on behalf of a subject/patient, to the subject's/patient's participation in the study.

The acquisition of informed consent and the subject's agreement or refusal of his/her notification of the primary care physician is to be documented in the subject's medical records, and the informed consent form is to be signed and personally dated by the subject or a legally acceptable representative and by the person who conducted the informed consent discussion. The original signed informed consent form is to be retained in accordance with institutional policy, and a copy of the signed consent form is to be provided to the subject or legally acceptable representative.

If a potential subject is illiterate or visually impaired and does not have a legally acceptable representative, the Investigator must provide an impartial witness to read the informed consent form to the subject and must allow for questions. Thereafter, both the subject and the witness must sign the informed consent form to attest that informed consent was freely given and understood.

Institutional Review Board (IRB)/Independent Ethics Committee (IEC)

A copy of the protocol, proposed informed consent form, as applicable, other written subject/patient information, and any proposed advertising material must be submitted to the IRB/IEC or other relevant ethical review board for written approval. A copy of the written approval of the protocol, and informed consent form, as applicable must be received by ICTU before the study can be initiated.

The Investigator must submit and, where necessary, obtain approval from the IRB/IEC or other relevant ethical review board for all subsequent protocol amendments and changes to the informed consent document, as applicable. The Investigator is to notify the IRB/IEC or other relevant ethical review board of deviations from the protocol or serious adverse event(s) occurring at the site and other safety event reports received from Amgen, in accordance with local procedures.

The Investigator is responsible for obtaining annual IRB/IEC or other relevant ethical review board approval /renewal throughout the duration of the study. Copies of the Investigator's reports, where applicable by local regulations and the IRB/IEC or other relevant ethical review board continuance of approval must be sent to ICTU.

